- Any unsolicited AEs within 28 days after the first vaccination were reported by 14.0% of participants in ARCT-154 group and 13.7% of participants in the placebo group. After the second vaccination, unsolicited AEs were reported by 13.9% and 15.9% of participants in the ARCT-154 and placebo groups, respectively. The majority of these events were not related to study vaccine.
- Serious AEs (SAEs) were reported by 118/8059 (1.5%) ARCT-154 recipients and 201/8041 (2.5%) placebo recipients in the Phase 3b stage within 92 days after the first vaccination (prior to switchero). Severe SAEs were reported by 20/8059 (0.2%) and 73/8041 (0.9%) of participants respectively. Related SAEs were reported by 10/8059 (0.1%) and 5/8041 (0.1%) participants in the ARCT-154 and placebo groups, respectively.
- From Day 92 (switchero) to Day 210, 88/7458 (1.2%) participants who received placebo after switchero, and 91/7353 (1.2%) participants who received ARCT-154 after switchero, reported at least one SAE. Severe SAEs were reported by 34/7458 (0.5%) and 23/7353 (0.3%) of participants, respectively. One related SAE (anaphylactic reaction that does not meet Brighton Collaboration criteria) was reported after switchero vaccination with ARCT-154 vaccine.
- No cases of myocarditis or pericarditis following administration of ARCT-154 or placebo were reported up to Day 210 post-vaccination.

In a Phase 1/2 clinical study ARCT-165-01, a booster dose of ARCT-154 induced a robust immune response in individuals who previously received the primary vaccination with a COVID-19 mRNA vaccine. Geometric fold increases of neutralizing antibodies (Day 29/pre-booster) against ancestral SARS-CoV-2 strain, and variants Beta, Delta, Omicron BA.1, BA.2, BA.4/5, BQ.1.1 and XBB.1.5 were 71, 87, 62, 49, 47, 33, 13, and 3, respectively. Neutralizing antibodies against various SARS-CoV-2 variants persist for at least 12 months post-booster dose.

In a Phase 3 clinical study in Japan (ARCT-154-J01), a booster dose of ARCT-154 elicited a noninferior immune response against Wuhan-Hu1 strain and superior immune response against Omicron BA.4/5 subvariant compared with the authorized mRNA vaccine (Comirnaty, Pfizer). The reactogenicity and safety profiles of both vaccines were similar, with no safety concerns raised.

Overall, clinical data for parent mRNA COVID-19 vaccines (ARCT-021, ARCT-154 and ARCT-165) support the favorable benefit-risk profile in adult participants.

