#### 3.3.2 Analysis of covariance

Analysis of covariance (ANCOVA) is a general linear model that evaluates whether the means of a dependent variable (DV) are equal across levels of one or more categorical independent variables (IV) and across one or more continuous variables (CV). Mathematically, ANCOVA decomposes the variance in the DV into variance explained by the CV(s), variance explained by the categorical IV, and residual variance (Keppel, G. (1991)).

The GMT ratio will be assessed using the ANCOVA model with treatment as factor and baseline antibody titer level (log-scale), age and sex as covariates, adjusted for the stratification factors from the CRF: number of previous doses and composition of last booster, if applicable. Two-sided 95% CIs for GMT ratio will be obtained by taking the anti-log of the confidence limits for

the adjusted mean difference of the logarithmically transformed assay results which is calculated using the t-distribution.

The general code to be executed in SAS for ANCOVA is as follows:

```
ODS OUTPUT LSMeanDiffCL = output_data_name;  
PROC GLM DATA=input_data;  
class Treatment Factor* sex**;  
model LogValue=Treatment Covariate# Factor* sex**/solution;  
lsmeans Treatment/pdiff cl;  
run;  
**sex as a categorical variable (Male, Female)  
#Covariate: age as a continuous variable, baseline antibody titers in log scale  
*stratification factors (not applicable when comparing the historical control group)  
1. number of previous COVID-19 vaccine doses (3 vs 4+)  
2. composition of the booster dose (original strain, bivalent/XBB1.5, unknown).
```

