### 3.9 Subgroup Analysis

Subgroup analysis for selected parameters including immunogenicity, solicited AEs, and unsolicited AEs will be performed for the second Final Analysis.

The following subgroups will be assessed for subgroup analysis (last 2 subgroups will be used for immunogenicity data only):

- Gender: Male or Female
- Race: White and Asian
- BMI:  $<30$  and  $\geq 30 \text{ kg/m}^2$
- Country: Australia, Philippines, Costa Rica and Honduras
- Ethnicity: Hispanic or Latino, not Hispanic or Latino
- Vaccine composition of last dose: ancestral, bivalent (BA.1 or BA.5 containing)
- Number of last COVID-19 doses: 3 doses or  $\geq 4$  doses

The descriptive summaries will be presented for subgroup analysis: Groups 2a and 2b combined vs Groups 3a and 3b combined for safety data; Groups 2a and 2b combined for immunogenicity data.

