## 13 APPENDIX

### 13.1 Sample Size Calculation

#### **STEP 1**

Objective 1:

The coprimary objective of simple superiority of the ARCT-2303 vaccine booster (groups 2a and 2b) compared to the ARCT-154 booster for the Omicron XBB.1.5 subvariant

Superiority of  $GMT_{ARCT-2303 \text{ (booster)}}$  to  $GMT_{ARCT-154 \text{ (booster)}}$

The superiority margin for the Omicron XBB.1.5 subvariant is defined as 1.0 for the GMTs ratio, thus the lower limit of the 2-sided 95% CI for GMT ratios (ARCT-2303/ARCT-154) is higher than 1.0.

Statistical power for the coprimary objective 1 is calculated assuming that:

- the GMT ratio between ARCT-2303 (Day 29) and ARCT-154 (booster; ARCT-154-J01 study) (Day 29) groups is 1.5,
- the common standard deviation is expected to be 0.60 in the log10 scale.

If the GMT ratio is 1.5 that means that the difference of the 2 means in log scale is 0.176 ( $\delta$ ). The differences between those two means is equal to 0 (=SM) when the GMT ratio is equal to 1.

Numeric Results for an Equal-Variance T-Test

Solve For:	Power						
Difference:	$\delta = \mu_1 - \mu_2 = Mt - Mr$						
Higher Means Are:	Better						
Hypotheses:	$H_0: \delta \leq SM \text{ vs. } H_1: \delta > SM$						
Power	N1	N2	N	SM	$\delta$	$\sigma$	Alpha
0.98768	500	350	850	0	0.176	0.6	0.025

Power	The probability of rejecting a false null hypothesis when the alternative hypothesis is true.
N1 and N2	The number of items sampled from each population.
N	The total sample size. $N = N_1 + N_2$ .
SM	The magnitude of the margin of superiority. Since higher means are better, this value is positive and is the distance above the reference mean that is required to be considered superior.
$\delta$	The difference between the treatment and reference means at which power and sample size calculations are made. $\delta = \mu_1 - \mu_2 = Mt - Mr$ .
$\sigma$	The assumed population standard deviation for each of the two groups.
Alpha	The probability of rejecting a true null hypothesis. One-sided Alpha=0.025 that is equivalent to Two-sided Alpha=0.05

The null ( $H_0$ ) and alternative ( $H_1$ ) hypotheses for one-sided tests are defined as

$H_0: \mu_1 - \mu_2 \leq \delta_0$  versus  $H_1: \mu_1 - \mu_2 > \delta_0$   
or equivalently

$H_0: \delta \leq \delta_0$  versus  $H_1: \delta > \delta_0$ .

Rejecting this test implies that the mean difference is larger than the value  $\delta_0$ .

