### Non-Inferiority

For coprimary objective 2 the assumption is that SCR is 50% in the reference method ( $p2 = 0.50$ ). If the SCR of the investigational is no less than 5 percentage points worse ( $\delta_0 = -0.05$ ) than the reference, it will be considered non-inferior. Substituting these figures into the statistical hypotheses gives

$$H0: p1 - p2 \leq -0.05 \text{ versus } H1: p1 - p2 > -0.05$$

The overall power for STEP 1 is calculated assuming that coprimary objectives 1 and 2 are independent; therefore overall power is 0.979 (0.98768\*0.99136) as stated in the protocol (section 10.2)

A sample size of up to 385 participants of study ARCT-154-J01, who received ARCT-154 vaccine booster, provided evaluable pre- and post-vaccination blood samples, and did not have SARS-CoV-2 infection and protocol deviations that impact on immunogenicity assessment (PPS-1), and up to 560 participants in the ARCT-2303 (groups 2a and 2b) provides approximately 99% power (n=350 and n=500 in the two groups if there is drop out of approximately 10%) to demonstrate each of the 2 coprimary objectives; therefore, there is at least 97% overall power to demonstrate the two coprimary objectives, 1 and 2.

### STEP 2

If coprimary objectives 1 and 2 are met, then the second step will be assessing the noninferiority of immune response after co-administration and standalone administration of ARCT-2303 and Flucelvax Quadrivalent vaccines. The following null hypotheses will be tested:

$$H03: \text{Day 29 GMT QIV}_{\text{QIV+ARCT-2303}} / \text{Day 29 GMT QIV}_{\text{QIV+Placebo}} \leq 0.67$$

(Group 1a vs 3a, i.e. co-admin group recipients vs standalone ARCT-2303 recipients)

$$H04: \text{Day 29 GMT ARCT-2303}_{\text{QIV+ARCT-2303}} / \text{Day 29 GMT ARCT-2303}_{\text{ARCT-2303+Placebo}} \leq 0.67$$

(Group 1a vs 2a, i.e. co-admin group recipients vs standalone Flucelvax recipients)

Statistical power is calculated assuming that:

- GMT ratios are expected to be 1.0
- the common standard deviation is expected to be 0.60 in the log10 scale.

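### In the historical comparison only (H01 and H06), the ANCOVA pools one residual variance over unequal, non-randomised groups of about 500 and 350; the confidence limits may be modestly off, more plausibly too wide than too narrow

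*SAP*

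**What the plan says.** SAP 3.3.2 gives one SAS template for every GMT ratio: PROC GLM with treatment, log baseline titer, age and sex, and limits from "lsmeans Treatment/pdiff cl". PROC GLM has a single residual mean square. The stratification factors (number of prior doses, composition of the last booster) are dropped when the comparator is the historical control.

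SAP 8.1.1 uses this model for H01 (lower limit above 1.0). SAP 8.1.5 reuses it for H06 (lower limit above 1.5).

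Equal variance appears only in the sample size appendix (SAP 13.1, Step 1). There "the common standard deviation is expected to be 0.60 in the log10 scale", and the power output is headed "Numeric Results for an Equal-Variance T-Test". The evaluable sizes are "n=350 and n=500 in the two groups if there is drop out of approximately 10" per cent, with 500 in the ARCT-2303 group and 350 in the ARCT-154 group. Neither document plans a variance check, a group-specific or robust variance, or an unequal-variance sensitivity analysis for this comparison.

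**The concern.** A pooled variance gives the right standard error for a difference of two means if the groups are equal in size or equal in variance. The Step 2 comparisons are planned at 360 per group, so they are protected. The historical comparison is not: it is planned at 500 against 350 (1.43 to 1), and neither randomisation nor a shared population gives a reason to expect equal residual spread.

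The two groups differ in several ways that could affect spread:
- **Country.** The controls come from a trial in Japan (Protocol 2.1.2). The current study lists "Country: Australia, Philippines, Costa Rica and Honduras" (SAP 3.9).
- **Vaccination history.** The controls had a primary series and one booster (Protocol 2.2). Groups 2a and 2b had 3 or 4+ doses, with a last booster that was original, bivalent/XBB1.5 or unknown (SAP 2.4). The terms for this history are left out of the model here.
- **Infection history.** The controls were anti-nucleoprotein seronegative (Protocol 2.2). The current study excludes COVID-19 or confirmed infection in the past 5 months, or ongoing sequelae (Protocol 5.2), and its schedule shows no such serology.

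H01 is one of the two tests that open the sequence (SAP 3.3.1), and SAP 3.4 relies on the hierarchy for multiplicity. Each test should therefore hold its nominal level. H06 rests on the same interval.

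**Working it through.** **Inputs from SAP 13.1 and its power paragraphs.** n1 = 500 (ARCT-2303), n2 = 350 (ARCT-154), log10 difference 0.176 for a ratio of 1.5, common SD 0.60, one-sided alpha 0.025.

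**The plan's own figure.** SE = 0.6 × √(1/500 + 1/350) = 0.0418. Power from the noncentral t with 848 df is 0.9876 (normal approximation 0.9877), against 0.98768 stated. It reproduces.

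**Effect of unequal SDs.** The documents give no group SDs, so the pairs below are assumptions.
- Pooled variance: sp² = [(n1−1)s1² + (n2−1)s2²] / (n1+n2−2)
- SE the model reports: √[sp²(1/n1 + 1/n2)]
- True SE: √(s1²/n1 + s2²/n2)
- R = reported SE / true SE
- Actual one-sided error = 1 − Φ(t × R), with t = 1.963

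Example, SDs 0.7/0.5: sp² = (499×0.49 + 349×0.25)/848 = 0.3912. Reported SE = 0.0436, true SE = √(0.49/500 + 0.25/350) = 0.0412, R = 1.059, and the error is 1 − Φ(2.079) = 1.9%.

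| SD ARCT-2303 / ARCT-154 | R | One-sided error |
|---|---|---|
| 0.6 / 0.6 | 1.000 | 2.5% |
| 0.65 / 0.55 | 1.030 | 2.2% |
| 0.6 / 0.5 | 1.032 | 2.1% |
| 0.7 / 0.5 | 1.059 | 1.9% |
| 0.6 / 0.4 | 1.070 | 1.8% |
| 0.55 / 0.65 | 0.971 | 2.8% |
| 0.5 / 0.6 | 0.969 | 2.9% |
| 0.5 / 0.7 | 0.944 | 3.2% |
| 0.4 / 0.6 | 0.934 | 3.3% |

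R depends only on the ratio of the SDs, so it does not matter that the residual SD after covariate adjustment may be below 0.60. With 360 per group R is 1.000 for any SD pair, which is why Step 2 is unaffected.

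**Check with covariates.** A 10,000-run simulation of the ANCOVA (baseline, age, sex) with the pooled SE gave 3.4% at 0.4/0.6 and 1.8% at 0.6/0.4. With a baseline shift of 0.4 between the studies it gave 3.2% and 1.8%. A heteroscedasticity-consistent SE gave 2.3% to 2.5% in the same four scenarios.

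**Power for H01 at a ratio of 1.5.** At SDs 0.7/0.5: 98.6% pooled, 99.0% with separate variances. At 0.5/0.7: 98.6% and 98.1%.

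**Power for H06.** The planning ratio of 1.5 is H06's null boundary, so a larger ratio must be assumed. Take 1.75: log10(1.75/1.5) = 0.0669. At SDs 0.7/0.5, 0.0669/0.04116 = 1.626. Pooled: Φ(1.626 − 2.079) = 32.6%. Separate variances: Φ(1.626 − 1.963) = 36.8%.

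**The case against.** The strongest reply is that this shows a possibility and not an error. The SAP states its equal-variance assumption openly and analyses accordingly. Nothing in the documents shows that the variances differ, and every departure above comes from assumed SDs. Titers are log-transformed and adjusted for baseline, age and sex. The control sera are retested together with the Group 2a and 2b samples (SAP 2.1), which limits assay-related differences in spread. H06 is a secondary test at the end of the sequence, with no power calculated for it (SAP 13.1, Step 3). The larger threat in this comparison is confounding.

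All of that stands, and it limits the weight of the point. It does not supply a reason to expect equal variance across two separate studies, and it does not make the pooled interval the safer choice.

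A reader might go further and infer that the pooled model inflates the false-positive rate of the test that opens the whole sequence. The documents do not support that. Inflation needs the smaller control group to be the more variable. What the documents describe is a control group from one country, with one prior booster and seronegative, against a mixed four-country group whose vaccination-history terms are left out of the model. That pattern suggests more spread in the larger group, and so conservative limits. It remains an inference, because no group SDs are given.

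**Conclusion.** The point holds as a modest, conditional one. For H01 and H06 the interval rests on an equal-variance assumption that is used in planning and not supported by data in either document, and the unequal group sizes mean the assumption matters.

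For assumed SD ratios up to 1.5, the standard error is off by up to about 7%. In the direction the documents suggest, the one-sided error is about 1.8% to 2.2%. H01 power is almost unchanged, and H06 loses a few points (about 4 in the worked case, which assumes a ratio of 1.75 and SDs 0.7/0.5). In the other direction the one-sided error is about 2.8% to 3.3%. If the SDs are equal there is no error.

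This does not show that the trial's main test is invalid or that its type I error is inflated. These figures assume the planned 500 and 350 evaluable participants.

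**What to change.** For SAP 8.1.1 and 8.1.5 only, keep the same covariates and base the 95% CI on group-specific residual variances. In SAS this is PROC MIXED with the same fixed effects, REPEATED / GROUP=Treatment, Satterthwaite degrees of freedom, and LSMEANS Treatment / DIFF CL. Report the pooled-variance result as a sensitivity analysis, and show the residual SD in each group so that a reader can see whether it mattered. Leave the equal-sized Step 2 models unchanged.

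The cost is a line or two of SAP wording and code. With equal SDs of 0.6, H01 power stays at 98.8%. If the Day 57 analysis has already been run, the pooled interval has to remain the prespecified one, and the group-specific interval should be added as a sensitivity analysis labelled as such.

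The change corrects the standard error only. Confounding from the non-randomised historical control is a separate matter that it does not touch.

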### **3.4 Multiple Comparisons and Multiplicity Adjustments.**

No adjustment for multiplicity is planned for this study due to the hierarchical testing strategy.

### **3.5 Handling of Missing Data**

For the classification of Treatment emergent adverse event (TEAE) and Concomitant medication, the following will be applied in the following order:

- a. If all dates/times (start and stop) are missing, the event/medication will automatically be classified as a TEAE/Concomitant medication.
- b. For AEs with a missing start date/time, if the event end date/time is prior to first study vaccine administration, the event will not be classified as a TEAE.
- c. If only the AE start year/ medication end year is present and is the same or is after the first study vaccine administration year unit, the event/medication will be classified as a TEAE/Concomitant medication.
- d. If the AE start month and year/medication end month and year are present and are the same or after the first study vaccine administration month and year units, the event/medication will be classified as a TEAE/Concomitant medication.

Missing results will not be imputed for all the immunogenicity and safety analyses.

### **3.6 Conversion of categorical values**

In some safety assessments, continuous variables are expressed as a range (i.e. < 10). In such cases, values may be converted to the range boundary (upper or lower limit as applicable). As an example, a value of <10 may be converted to 10. Such substitutions will be clearly documented in the footnotes of relevant outputs.

For the calculation of GMT and GMFR, imputation will be applied. Antibody titer values above the upper limit of quantitation (ULOQ) will be set to ULOQ, while antibody titer values below the lower limit of quantitation (LLOQ) will be imputed as ½ LLOQ (i.e., 0.5\*LLOQ).

### **3.7 Coding of Events and Medications**

Medical history, Surgical and Medical Procedure and AE verbatim terms will be coded using the Medical Dictionary for Regulatory Activities (MedDRA) using the latest version available at

the time of study commencement. Terms will be coded to the full MedDRA hierarchy, but the system organ class (SOC) and preferred terms (PT) will be of primary interest for the analysis.

Prior and concomitant medications will be coded using the World Health Organization Drug Dictionary (WHO-DD) using the latest version available at the time of study commencement. Medications will be mapped to the full WHO-DD Anatomical Therapeutic Chemical (ATC) class hierarchy, but PTs will be of primary interest in this analysis.

### 3.8 Treatment Groups

Group 1a: ARCT-2303 + QIV  
Group 2a: ARCT-2303 + Placebo  
Group 3a: QIV + Placebo  
Group 1b: ARCT-2303 + aQIV  
Group 2b: ARCT-2303 + Placebo  
Group 3b: aQIV + Placebo  
ARCT-2303 (Gr 2a and 2b)  
QIV/aQIV (Gr 3a and 3b)  
ARCT-154

If any actual treatments received cannot belong to any one of the treatment groups above (e.g. subject receives only one injection), the participant will be summarized under the randomized treatment group.

### 3.9 Subgroup Analysis

Subgroup analysis for selected parameters including immunogenicity, solicited AEs, and unsolicited AEs will be performed for the second Final Analysis.

The following subgroups will be assessed for subgroup analysis (last 2 subgroups will be used for immunogenicity data only):

- Gender: Male or Female
- Race: White and Asian
- BMI:  $<30$  and  $\geq 30 \text{ kg/m}^2$
- Country: Australia, Philippines, Costa Rica and Honduras
- Ethnicity: Hispanic or Latino, not Hispanic or Latino
- Vaccine composition of last dose: ancestral, bivalent (BA.1 or BA.5 containing)
- Number of last COVID-19 doses: 3 doses or  $\geq 4$  doses

The descriptive summaries will be presented for subgroup analysis: Groups 2a and 2b combined vs Groups 3a and 3b combined for safety data; Groups 2a and 2b combined for immunogenicity data.

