4.1 Overall Design

Approximately 1680 participants will be enrolled in this study.

Study arms and vaccination schedule:

Participants who received at least 3 doses (a 2-dose primary series and at least one booster dose) of the US-authorized mRNA COVID-19 vaccines, with the last mRNA booster dose (original strain or bivalent) ≥ 5 months before enrollment will be recruited in one of the two cohorts.

Cohort A (participants 18 to 64 years of age; N=1200)

Individuals will be randomly assigned to one of the three study groups:

- Group 1a (ARCT-2303/ Flucelvax Quadrivalent, N=400): participants will receive one dose of ARCT-2303 and one dose of Flucelvax Quadrivalent (opposite arms) on Day 1, and one dose of placebo on Day 29.
- Group 2a (ARCT-2303, N=400): participants will receive one dose of ARCT-2303 and one dose of placebo (opposite arms) on Day 1, and one dose of Flucelvax Quadrivalent on Day 29.
- Group 3a (Flucelvax Quadrivalent, N=400): participants will receive one dose of Flucelvax Quadrivalent and one dose of placebo (opposite arms) on Day 1, and one dose of ARCT-2303 on Day 29.

Cohort B (participants ≥ 65 years of age; N=480)

Individuals will be randomly assigned to one of the three study groups:

- Group 1b (ARCT-2303/ Fluad Quadrivalent, N=160): participants will receive one dose of ARCT-2303 and one dose of Fluad Quadrivalent (opposite arms) on Day 1, and one dose of placebo on Day 29.
- Group 2b (ARCT-2303, N=160): participants will receive one dose of ARCT-2303 and one dose of placebo (opposite arms) on Day 1, and one dose of Fluad Quadrivalent on Day 29.
- Group 3b (Fluad Quadrivalent, N=160): participants will receive one dose of Fluad Quadrivalent and one dose of placebo (opposite arms) on Day 1, and one dose of ARCT-2303 on Day 29.

In addition, all available serum samples from study participants of study ARCT-154-J01, who received a booster dose of candidate ARCT-154 vaccine according to the protocol, provided pre- and post-vaccination blood samples and did not have evidence of SARS-CoV-2 infection and major protocol deviations, will be selected to use as a comparator. This set of samples will

CONFIDENTIAL

compose up to 385 individuals 18 years of age and above, who were included in the per protocol set 1 (PPS-1). These samples will be tested in this study for assessment of coprimary study objectives 1 and 2.

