8.10.1 Blood Volumes and Serological Testing

All analyses will be performed at a laboratory designated by the Sponsor or the Sponsor's designee using standardized and validated procedures.

The maximum volume of blood taken at any single visit is 30 mL, and the maximum total volume of blood collected during the study period in each study participant is approximately 90 mL. All samples listed in [Table 6](#) will be drawn in all participants.

On Days 1 and 29, all samples from prespecified study arms will be tested using VNA with Omicron XBB.1.5 subvariant, and hemagglutination inhibition assay. A random subset of samples from Groups 2a and 2b will be tested using VNA to assess antibody persistence at Day 181 and to evaluate cross-neutralization of epidemiologically relevant variants of SARS-CoV-2 on Days 1 and 29. The random selection process of samples will be described in the Statistical Analysis Plan.

In case of lack of agglutination for a specific strain using the HI assay, a microneutralization assay will be used for the respective strain.

The testing plan is provided in [Table 6](#).

CONFIDENTIAL

Table 6 Testing Plan for ARCT-2303-01

| Assay | Study Arms | Day 1 N | Day 29 N | Day 181 N |
|---|--|---|--|---|
| VNA (Omicron XBB.1.5) | Group 1a Group 1b Group 2a Group 2b ARCT-154-J01 study | 400 (all) 160 (all) 400 (all) 160 (all) ~385 | 400 (all) 160 (all) 400 (all) 160 (all) ~385 | — — 100 (subset) 100 (subset) — |
| Hemagglutination Inhibition assay (H1N1, H3N2, 2B) | Group 1a Group 1b Group 3a Group 3b | 400 (all) 160 (all) 400 (all) 160 (all) | 400 (all) 160 (all) 400 (all) 160 (all) | — — — — |
| Microneutralization assay (H1N1, H3N2, 2B) | Group 1a Group 1b Group 3a Group 3b | In case of lack of agglutination for a specific strain using HI assay | | — |
| VNA (various lineages, including any prevalent variant) | Group 2a | 50 (subset) | 50 (subset) | — |
| Total maximum volume/ each participant | | 30 mL | 30 mL | 30 mL |

Abbreviations: N: number of participants per timepoint; VNA, virus neutralizing assay; Safety testing may be performed in case of suspected myocarditis or pericarditis or other safety concerns

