## 8 IMMUNOGENICITY

All Immunogenicity analyses will be done using the PP set. For secondary immunogenicity objectives 3, 4, 5 and 6, if more than 5% participants are excluded from PP set as compared to mITT set, then the analysis will be repeated for the mITT analyses set.

Humoral immune responses against Omicron XBB.1.5 subvariant will be assessed by means of Virus Neutralizing assay (VNA) in Groups 1a and 1b, Groups 2a and 2b, and in samples (Days 1 and 29) from ARCT-154 recipients, included in the PPS-1 in study ARCT-154-J01.

Humoral immune responses against QIV and aQIV will be assessed by means of Hemagglutination Inhibition assay (H1N1, H3N2, two B strains, separately) will be assessed in Groups 1a and 1b, and Groups 3a and 3b. In case of lack of agglutination for a specific strain using HI assay, immunogenicity for that strain will be assessed as measured by microneutralization assay as an acceptable alternative.

The per protocol (PP) set will be used for the primary objectives to assess superiority and noninferiority. PPS and PPS1 will be used for primary objectives 1 and 2, whereas PPS will be used for primary objectives 3 and 4.

The GMT ratio for each of the primary immunogenicity endpoints will be assessed by using analysis of covariance (ANCOVA) model that will include covariates and stratification factors (see Section 3.3.2). Two-sided 95% CIs for GMT ratio will be obtained by taking the antilog of the confidence limits for the adjusted mean difference of the logarithmically transformed assay results which is calculated using t-distribution.

Descriptive immunogenicity analysis including GMT, GMFR, and SCR will be produced for each group at all available time points, along with the 95% CIs.

Geometric mean will be calculated as the mean of the antibody results after the data are log-transformed and then taking the antilog of the log-mean to present the results on the original scale. Two-sided 95% CI will be obtained by taking the log transformation of the antibody results and calculated based on t-distribution and then taking the anti-log of the confidence limit. For the calculation of GMT and GMFR, imputation will be applied to antibody titer values above the upper limit of quantitation; ULOQ will be used. Antibody titer values below the lower limit of quantitation will be imputed as  $\frac{1}{2}$  LLOQ (i.e., 0.5\*LLOQ).

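### A pooled Group 2a+2b summary at Day 181 would be half aged 65 and over, against 28.6% at Days 1 and 29, because the persistence subset is drawn unequally and the SAP gives no weights

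*SAP*

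**What the plan says.** **Sampling.** Protocol 4.1 puts 400 participants aged 18 to 64 in Group 2a and 160 aged 65 and over in Group 2b. Protocol 8.10.1, Table 6, tests all of them against XBB.1.5 on Days 1 and 29. For Day 181 the entries for the two groups read "100 (subset) 100 (subset". The text of that section says: "A random subset of samples from Groups 2a and 2b will be tested using VNA to assess antibody persistence at Day 181". It adds: "The random selection process of samples will be described in the Statistical Analysis Plan".

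**Pooling.** SAP 3.8 lists Groups 2a and 2b separately and also the combined group "ARCT-2303 (Gr 2a and 2b". SAP 3.9 schedules subgroup analyses for the second final analysis (sex, race, BMI, country, ethnicity, composition of the last dose, number of doses) and presents them as "Groups 2a and 2b combined for immunogenicity data". Age is not among the subgroups.

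**Estimation.** SAP 8 says: "Descriptive immunogenicity analysis including GMT, GMFR, and SCR will be produced for each group at all available time points". SAP 8.2 lists the GMT at Days 1, 29 and 181. The GMT in SAP 8 is an unweighted log-mean, back-transformed. SAP 4.1.4 defines a PP (Day 181) set made up of the tested subset. The SAP contains no sampling weights, no age standardisation and no description of how the subset is drawn.

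**The concern.** The two age cohorts enter the Day 181 subset at different rates, so a pooled Day 181 figure describes a different age mix from the pooled Day 29 figure. If titers differ by age, the pooled Day 181 GMT moves for a reason unrelated to persistence. A reader who sets it beside the Day 29 GMT of the full per-protocol set would take a change in composition for a change in antibody level. Protocol 2.2.1 names six-month persistence as something the study will assess. The subgroup tables are the most exposed, because SAP 3.9 plans them only for the pooled group and no by-cohort version would reveal the shift.

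**Working it through.** **Inputs.** Group sizes 400 and 160 (Protocol 4.1); Day 181 samples 100 and 100 (Protocol Table 6). The pooled size reproduces the plan's own figure: 400 + 160 = 560 (Protocol 10.2). The documents give no titers by age for ARCT-2303, so the older/younger GMT ratio r is an assumption and is shown as a range.

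**Step 1: age mix.**
- Sampling fractions: 100/400 = 25.0% and 100/160 = 62.5%.
- Share aged 65 and over, Days 1 and 29: 160/560 = 28.6%. With 10% dropout in both groups it is unchanged: 144/504 = 28.6%.
- Share aged 65 and over, Day 181 subset: 100/200 = 50.0%.

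**Step 2: effect on the pooled Day 181 GMT.** A pooled log-mean is the share-weighted average of the two cohort log-means. So unweighted GMT / GMT at the 400:160 mix = r^(0.500 − 0.286) = r^0.214, with r taken at Day 181.

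| Assumed r | Factor |
|---|---|
| 0.5 | 0.86 |
| 0.7 | 0.93 |
| 0.8 | 0.95 |
| 1.0 | 1.00 |
| 1.25 | 1.05 |

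**Step 3: effect on a Day 181/Day 29 comparison.** This depends on which participants supply Day 29.
- Full Day 29 set beside the unweighted Day 181 subset: the error is the same factor, r^0.214.
- Same subset at both visits: the error is (r at Day 181 / r at Day 29)^0.214. It is exactly 1.00 if both cohorts wane equally, 0.94 if r falls from 0.67 to 0.5, and 1.07 if r rises from 0.5 to 0.67.

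**Step 4: subgroups.** If a subgroup's full-set share aged 65 and over is p, random sampling within cohort gives an expected Day 181 share of 2.5p/(1 + 1.5p), where 2.5 = 0.625/0.25. At p = 0.286 this returns 50%. The exponent therefore varies between subgroups with their age mix.

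**Step 5: weighting.** Inverse sampling fractions are 400/100 = 4.0 and 160/100 = 1.6. The weighted older share is 160/(400 + 160) = 28.6%. Effective n = (100×4.0 + 100×1.6)² / (100×4.0² + 100×1.6²) = 313,600/1,856 = 169, against 200. CI width on the log scale grows by √(200/169) = 1.09.

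**The case against.** A reader might infer that the pooled result overstates waning from Day 29. The documents do not support that. It would need lower titers in older participants together with a full-set Day 29 comparator, or faster waning in older participants, and the documents establish none of these. The error is nil at r = 1 and reverses above 1. The SAP does not say whether Day 29 values shown beside Day 181 come from the full PP (Day 29) set or from the Day 181 subset. Nor does it define a Day 181/Day 29 measure: the GMFR is within participant and against baseline, so the age mix cannot differ between its numerator and denominator. These objections stand.

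It can also be said that SAP 3.9 names no time point and that the pooled group has other uses, namely coprimary objectives 1 and 2 at Day 29 and the Day 1 safety summaries. This stands in part: pooled Day 181 reporting is an inference. It is a strong one. SAP 1 and 10.2 make the second final analysis the analysis of Day 181 immunogenicity, and Day 181 is the only scheduled immunogenicity sample after Day 57.

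Secondary objectives 3 and 5 already place Day 181 under Groups 2a and 2b separately. That limits the damage for the overall result but does not reach the subgroup tables.

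Finally, 400:160 is an enrolment quota, and no document makes it the target mix for Day 181. That is fair. The case for weighting to it is comparability with the Day 29 pool. Reporting by cohort avoids choosing a mix at all.

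**Conclusion.** The composition shift is real and follows from the plan's own counts: 50% against 28.6% aged 65 and over. Its consequence is conditional. Over assumed r from 0.5 to 1.25, a pooled unweighted Day 181 GMT, or its ratio to a full-set Day 29 GMT, is off by a factor of 0.86 to 1.05 relative to the 400:160 mix, and the direction cannot be stated in advance. This rests on the Table 6 numbers being achieved, on pooled Day 181 summaries being produced, and on the assumed range of r. No hypothesis test, success criterion or coprimary objective is touched, since all six hypotheses use Day 29. The point is a modest, inexpensive correction to descriptive reporting. Separately, the SAP leaves out the selection method that Protocol 8.10.1 assigns to it, whatever the titers turn out to be.

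**What to change.** In SAP 3.9 and 8.2:
- Present Day 181 results by age cohort, or weight any pooled 2a+2b Day 181 summary, subgroups included, by inverse sampling fraction: 4.0 for Group 2a and 1.6 for Group 2b, updated to the fractions actually achieved.
- Take Day 29 values shown beside Day 181 from the same participants, and say so in the table.
- Describe how the Day 181 subset is drawn, including the different fractions by cohort.

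The cost is SAP wording and one weight variable. Weighting reduces the effective n from 200 to about 169 and widens the pooled confidence interval by roughly 9%. By-cohort reporting needs no weights but rests on about 100 participants per cohort, and fewer in each subgroup.
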